## Abstract

**Background:** Dystonia is a relatively rare group of movement disorders that often prove difficult to treat effectively. Nowadays, deep brain stimulation (DBS) has become widespread and established treatment for patients with dystonia. The bilateral stimulation of either the globus pallidus internus (GPi) or the subthalamic nucleus (STN) is effective and safe in improving clinical symptoms and quality of life for patients with dystonia. RELAX study is a multicenter, prospective, randomized study designed to evaluate the clinical effectiveness and safety of DBS in patients with dystonia.

**Methods/Design:** Participants will be recruited in approximately 10 centers across China. All patients will undergo genetic testing. Eligible participants with dystonia will undergo DBS implantation according to the target randomization. Then, participants will be randomized to one of two groups: the experimental group (EG) with DBS on or the control group (CG) with DBS off. The primary outcome measures will focus on the changes in the Burke-Fahn-Marsden Dystonia Rating Scale (BFMDRS) movement scores, specifically assessed at three and six months of treatment. Secondary outcome measures, including specific item scores on the Short-Form General Health Survey (SF-36), Visual Analog Scale (VAS), walking measurements, the Beck Depression Inventory (BDI), Mini-Mental State Examination (MMSE), and the rate of improvement of the BFMDRS score, were all observed and recorded at 3 and 6 months during the treatment period. The aim of this trial is to investigate the efficacy and safety of DBS in patients with primary dystonia and gain insight regarding the therapeutic effects of different targets. **Discussion:** This is a large sample, randomized controlled trial to comprehensively evaluate the effectiveness and safety of DBS in patients with dystonia of different target.

**Trial registration:** NCT03017586, clinicaltrials.gov, registered on January 11, 2017, <https://www.clinicaltrials.gov/ct2/show/NCT03017586>

**Keywords:** Dystonia, Deep brain stimulation, Subthalamic nucleus, Globus pallidus internus

## **Background**

Dystonia is the third most common movement disorder, characterized by sustained or intermittent involuntary muscle contractions causing twisting and repetitive movements or abnormal postures [1]. Primary dystonia is the most common form of dystonia, comprises a group of idiopathic, incurable movement disorders that vary with respect to age at onset, body distribution, and genetic association, to be 16.4 per 100,000 individuals [2]. Primary dystonia is a severe motor disease, causing physical and social incapacity in patients, devastating with significant morbidity and mortality [3]. Botulinum toxin is recommended as first-line treatment for dystonia, but its efficacy is variable and may wane over time. Besides, botulinum toxin is useful in focal dystonia but is difficult to use in generalized dystonia. The pharmacological treatment of dystonia is more challenging, bearing poor results [4]. The deep brain stimulation (DBS), available since the late 1980s, has become more widespread and now has established efficacy in a range of medically refractory movement disorders, such as Parkinson's disease (PD) and essential tremor (ET) [5]. DBS for treatment of dystonia was approved by the US Food and Drug Administration under a Humanitarian Device Exemption in 2003 [2]. DBS is now applied worldwide and the benefit-to-risk ratio of the therapy for dystonia is under scrutiny [6]. Typically, the globus pallidus internus (GPI) is the primary and the most studied target in dystonia. Recently, subthalamic nucleus (STN) stimulation has also shown a good response rate [4]. Studies have demonstrated that either the GPI or the STN is effective and safe in improving clinical symptoms and quality of life for patients with dystonia [7]. To our knowledge, however, only few studies have directly compared the clinical effects of GPI and STN stimulations in patients with dystonia, and best target for DBS in dystonia is still unknown [7]. Thus, randomized controlled trial (RCT) evidence is needed to confirm the efficacy and safety of DBS in dystonia patients, gain insight regarding the therapeutic effects of different targets (STN and GPI). To this end, we designed present multicenter, prospective, randomized and controlled study in patients with primary dystonia.

## **Aims**

The purpose of this study is to evaluate the safety and effectiveness of deep brain stimulation (DBS) of the subthalamic nucleus (STN) and globus pallidus internus (GPI) for primary dystonia.

## **Design and Methods**

### **Trial design**

The RELAX study (ClinicalTrials.gov ID: NCT03017586) is a double blind, randomized, multicenter trial designed to evaluate the clinical effectiveness and safety of DBS using new device (G104, E202, L301/L302, PINS, Inc., Beijing, BJ, China) on patients with primary dystonia. Based on strict inclusion and exclusion criteria, patients with dystonia will undergo rigorous screening for the study. A total of five follow-up surveys have been arranged for the research. After recruitment, in the follow-up V2, participants will undertake the implantation of lead and IPG according to the target randomization. After the implantation, participants will be randomized (1:1) to one of two groups: the experimental group (EG) or the control group (CG). The IPG of participants in EG will be turned ON, the IPG of participants in CG will be turned OFF for 3 months. After 3 months of stimulation in the blinded conditions, unblinding, the IPG of participants will turn ON and receive follow-up assessments for another 3 months. The clinical measurements for the two groups include the Burke-Fahn-Marsden Dystonia Rating Scale (BFMDRS), the Short-Form General Health Survey (SF-36), the Beck Depression Inventory (BDI) et al. All outcomes will be calculated by blinded statisticians appointed by clinical research institute of Peking University following the end

of the trial. The protocol design is based on the guidelines of the Consolidated Standards of Reporting Trials (CONSORT) and Standard Protocol Items: Recommendations for Interventional Trials (SPIRIT), and the study results will also be reported according to these guidelines. Informed consent will be obtained from all participants in accordance with the policies of the board.

### **Study setting**

The trial will be conducted at approximately 10 investigative centers domestically. Other hospitals will be invited to join the study according to interest, feasibility, and resources. No single center could exceed 30% of all enrolled patients. The clinical investigators from each center will be responsible for screening eligible participants. The protocol has been approved by the Clinical Trial Ethics Committee of Peking Union Medical College Hospital and registered on ClinicalTrials.gov protocol system (Clinical Trials Identifier: NCT03017586).

### **Patient population and recruitment**

The study population comprises 70 patients suffering from primary dystonia. A patient must meet all of the inclusion criteria and none of the exclusion criteria to be eligible for the study. A neurologist specialized in movement disorders will assess the patients' eligibility for study participation.

### **Inclusion and exclusion criteria**

In detail, the key inclusion criteria are:

1. Refractory primary (systemic, segmental) dystonia diagnosed by a movement disorders neurologist
2. Severe functional impairment despite optimal medical management, including failed botulinum toxin therapy
3. Ability to follow up with post-operative study visits
4. Patients and their relatives have reasonable surgery expectations
5. Volunteer to participate in clinical trials, and signed consent form
6. Age 6-60 years

Exclusion criteria are:

1. Pregnancy or plan a pregnancy
2. Good treatment with Non-invasive therapy
3. Dopamine reactive dystonia , Genetic degeneration , Paroxysmal dystonia , Secondary dystonia, Psychogenic dystonia
4. Brain MRI showing extensive brain atrophy or small vessel ischemic disease
5. Cognitive impairment(MMSE<24)
6. Severe depression or other serious mental illness
7. History of traumatic brain injury, tumor, or severe cerebrovascular disease
8. Severe brain atrophy (diagnosed by CT or MRI)
9. Hyperthermia therapy in implant parts
10. Abnormal in blood inspection, blood clotting disorders, liver and kidney dysfunction, or other clinical judgment cannot tolerate surgery
11. High blood pressure, serious heart diseases, or respiratory diseases
12. Diabetes
13. Long-term treatment of immunosuppressive or hormones

14. Implant pacemakers, defibrillators, cochlear and other nerve stimulators
15. Other diseases need frequent MRI examinations
16. Participated in any other clinical trials within 3 months
17. Reluctant or unable to implant surgery
18. Reluctant or unable to cooperate with follow-up
19. Other exclusion Criteria by researchers

### **Recruitment of participants**

Participants will be recruited by placing advertisements and posters in clinics and directly at the participating centers. The recruitment information mainly includes eligibility criteria and contact details. A well-trained investigator in each participating center will be responsible for screening all potentially eligible patients based on the eligibility criteria and obtaining the informed consent.

### **Randomization and blinding**

There are two step of randomization allocation in this study. Firstly, eligible participants will be randomly assigned to one of two targets (STN or GPi) after completing the baseline measurements. The random numbers will be used to create the participant numbers and order lists, which will be placed in opaque sealed envelopes and sent to the research centers. After implantation of the device, participants will be randomly assigned to one of two groups (EG group or CG group). The participants randomized to the EG undergoing the DBS stimulation, participants in the CG will be OFF the DBS stimulation for 3 months follow-up. The assignment sequence (based on computer-generated random numbers) will be produced by The Peking University Clinical Research Institute. The research clerk will keep copies of the order lists and participant numbers.

Throughout the study, with the exception of the study programmer, all participants and study staff (including investigators, trainers, and statisticians) will be blinded to the treatment allocation. Independent raters who have no therapeutic relationships with the participants and who are blind to the treatment conditions will conduct outcome assessments. The independent raters will be clinical neurologists who have received additional training on the use of the outcome assessments, had the opportunity to listen to conducted assessments, and received direct feedback regarding their assessments from supervisors. Loss of blinding may occur due to the magnitude of the therapeutic effect or any other subjective perception.

### **Outcomes measures**

#### **Primary clinical outcomes**

The primary outcome measures will focus on the changes in movement scores on the Burke-Fahn-Marsden Dystonia Rating Scale (BFMDRS), which will be specifically assessed after three and six months of treatment.

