#### **Sample size and power calculations**

The study concerns the improvement of dystonia between EG and CG in terms of BFMDRS score in the 3 months follow-up. According to the results of study, which design is basically the same as this trial. With a power setting of 80% and calculations based on two-sided 95% confidence intervals, the study required 17 pairs for GPi and 14 pairs for STN. We assume that 10% of the trial participants will be lost to attrition. Thus, a total of 70 participants need to be allocated to each treatment group.

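### Months 3 and 6 are both primary and unranked, but only month 3 has an OFF control and a sample-size basis

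*Protocol*

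**What the plan says.** - **Primary outcome.** The Primary clinical outcomes section takes change in BFMDRS movement score, "which will be specifically assessed after three and six months of treatment". The Abstract does the same: "specifically assessed at three and six months of treatment". Neither ranks the two time points or says which groups are compared at each.
- **Sample size.** The Sample size and power calculations section describes one comparison at one time: "The study concerns the improvement of dystonia between EG and CG in terms of BFMDRS score in the 3 months follow-up". At 80% power and a two-sided 5% level, "the study required 17 pairs for GPi and 14 pairs for STN". It then allows for 10% attrition and reaches 70.
- **Control period.** Under Randomization and blinding, "participants in the CG will be OFF the DBS stimulation for 3 months follow-up". Under Trial design, once that period ends, "the IPG of participants will turn ON and receive follow-up assessments for another 3 months".
- **Testing.** The Statistical analysis section sets one threshold, p < 0.05.
- **Blinding.** Trial design reads: "After 3 months of stimulation in the blinded conditions, unblinding, the IPG of participants will turn ON". The blinding statement under Randomization and blinding begins "Throughout the study, with the exception of the study programmer, all participants and study staff" and has no end date.

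**The concern.** The sample size section indicates that month 3 was meant to decide the trial, yet the primary outcome as written gives month 6 the same standing. The two time points answer different questions. At month 3 the randomised comparison is stimulation against no stimulation. At month 6 everyone is stimulated, so EG versus CG is longer against shorter stimulation, and change from baseline has no control at all.

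Two misreadings follow. A small EG versus CG difference at month 6 may mean only that the CG has caught up, yet it would count as a missed primary time point. Conversely, a large month-6 change from baseline, which mixes stimulation with any other source of change over time, could be reported as a primary result of a randomised trial.

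The description of the time points as months of treatment also does not fit the CG, which has had no stimulation at month 3 and about three months of it at month 6.

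**Working it through.** **1. Reproducing the target of 70.** The inputs are 17 and 14 pairs, 10% attrition and 1:1 allocation. Read a pair as one EG plus one CG patient.

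- GPi: 17/0.9 = 18.9, rounded up to 19 per arm
- STN: 14/0.9 = 15.6, rounded up to 16 per arm
- Total: 2 × (19 + 16) = 70

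The figure follows from the month-3 comparison alone and holds no allowance for a second primary time point. The 17 and 14 themselves cannot be rebuilt, because the protocol gives neither the effect nor the SD.

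**2. Stimulation received by each visit** (Trial design; Randomization and blinding).

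| Visit | EG | CG | EG versus CG compares |
|---|---|---|---|
| Month 3 | 3 months | 0 months | ON with OFF |
| Month 6 | 6 months | 3 months | longer with shorter ON |

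**3. Month-3 effect implied by the sizing.** For a two-sample t-test (noncentral t, two-sided 5%, 80% power), solve for the standardised difference d:

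- 17 per arm: d = 0.991
- 14 per arm: d = 1.100
- pooled, 31 per arm: d = (17 × 0.991 + 14 × 1.100)/31 = 1.040, giving 98% power at month 3

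The protocol does not say whether the primary test is per target or pooled, so both are carried forward.

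**4. Illustrative power of EG versus CG at month 6.** These assumptions are not in the protocol:

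- the SD is constant;
- the CG benefit at month 6 equals the EG benefit at month 3 (full catch-up);
- f is the share of the EG's six-month benefit already reached by month 3.

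The EG benefit at month 6 is then d/f and the CG benefit is d, so the difference is d(1/f − 1). For f = 0.8, 1/f − 1 = 0.25: the difference is 0.991 × 0.25 = 0.248 for GPi and 1.040 × 0.25 = 0.260 pooled.

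| f | Per target | Pooled | Per target, slower CG | Pooled, slower CG |
|---|---|---|---|---|
| 0.9 | 6% | 7% | 14% | 24% |
| 0.8 | 11% | 17% | 24% | 44% |
| 0.7 | 22% | 41% | 42% | 72% |
| 0.6 | 46% | 77% | 68% | 94% |
| 0.5 | 80% | 98% | 92% | 100% (99.8%) |

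The last two columns let the CG reach only 80% of the EG's month-3 benefit, so the difference becomes d(1/f − 0.8).

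Power falls below 80% once f exceeds these limits:

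- full catch-up: 0.50 per target, 0.59 pooled
- slower CG: 1/1.8 = 0.56 per target, 1/1.495 = 0.67 pooled

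The per-target limit of 0.50 is true by construction, since 1/f − 1 = 1 at f = 0.5. The 17 and 14 per-arm cases also agree by construction.

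**5. Error rate, only if success at either time point sufficed at 0.05.** With both null hypotheses true, the familywise error is 1 − P(|Z₁| < 1.96 and |Z₂| < 1.96). Under a bivariate normal this is 9.1%, 8.3% and 7.0% at assumed correlations 0.5, 0.7 and 0.9. The protocol states no rule for combining the time points.

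**6. Cost of keeping both as EG versus CG tests, either sufficing.** Splitting alpha to 0.025 each (normal approximation) lowers month-3 power per target from 80% to about 71%. Restoring 80% needs 21 and 17 pairs. With attrition, 21/0.9 rounds up to 24 and 17/0.9 to 19, so the total is 2 × (24 + 19) = 86.

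**The case against.** The strongest counter-argument is that month 6 was never meant as an EG versus CG test. Target is randomised too, and with all devices on at month 6, STN versus GPi is a concurrent randomised comparison that needs no OFF control. The Abstract and Discussion both express interest in comparing targets. On this view the power table tests a hypothesis the protocol does not state, the error rates assume a success rule it does not contain, and any ordering of time points may sit in the SAP. The treatment wording could also mean time within the study's treatment period, as the secondary outcomes section has it.

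Much of this limits the argument without removing it. The power and error figures are conditional illustrations, and the lack of a multiplicity rule in the protocol is not in itself a fault. The months-of-treatment wording may simply be loose. But the primary outcome section does not name STN versus GPi, and no power is stated for that comparison either. A testing order in the SAP cannot create an OFF control at month 6. The mismatch between the primary outcome and the sizing is in the protocol itself.

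**Conclusion.** The point stands and should be fixed. The protocol makes month 6 primary on equal terms with month 3, while its own sizing covers month 3 only and its own design ends the OFF control there. That rests on the text alone and is firm.

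The size of the consequence is less certain. With full CG catch-up, month-6 EG versus CG power runs from 6% to 80% per target and from 7% to 98% pooled as f goes from 0.9 to 0.5. It would therefore be poor if most of the benefit arrives within three months, and adequate if much of it arrives later. The assumed catch-up, constant SD and reading of pairs all enter these figures. The month-3 comparison and its stated power are not affected.

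A separate, smaller point does not drive this conclusion: the protocol announces unblinding after month 3 without saying who is unblinded, while elsewhere it describes blinding as lasting the whole study.

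**What to change.** 1. In the Abstract and the Primary clinical outcomes section, name one primary outcome: change in BFMDRS movement score from baseline to month 3, EG versus CG.
2. Make month 6 secondary, reported with 95% confidence intervals. Useful analyses are the CG change from month 3 (OFF) to month 6 (ON), maintenance in the EG from month 3 to month 6, and the randomised STN versus GPi comparison adjusted for EG/CG.
3. Describe visits by months since randomisation, and give months of stimulation separately for each group.
4. Make the amendment before anyone deciding on it has seen unblinded outcome results, including any outcome summary given to the DSMB. State this, with the date, in the amendment. Check the registry entry, which was not available here, and bring it into line.
5. Separately, reconcile Trial design with Randomization and blinding: say who is unblinded after month 3, and that the independent raters remain unaware of EG/CG allocation through the month-6 rating.

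**Cost.** Removing a primary time point while the trial is enrolling is a substantive change that needs ethics approval, although the edit itself is short. Month 6 loses primary status. The target of 70, the 0.05 level, the stated 80% power and the visit schedule are unchanged.

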#### **Secondary clinical outcomes**

Secondary outcome measures, including specific item scores on the Short-Form General Health Survey (SF-36), Visual Analog Scale (VAS), walking measurements, the Beck Depression Inventory (BDI), Mini-Mental State Examination (MMSE), and the rate of improvement of the BFMDRS score, were all observed and recorded at 3 and 6 months during the treatment period.

#### **Safety outcomes**

The occurrence rate of adverse events (AEs)/serious adverse events (SAEs) are documented at the scheduled and unscheduled clinical visits will be used to evaluate the safety of DBS. The

investigators are responsible for the management of participants' AEs and SAEs. During assessments, the investigator will question the participants about the occurrence of AEs and record the information in the source documents and patient case report form (CRF). The clinician will turn off the DBS therapy and evaluate the vital signs of the participant if the SAE occurs, then the suited therapy would be given for the participant. The investigators may choose hospitalization, outpatient treatment, home visits, communication, or other follow-up methods. All incidents are reported to the regulatory authority. All safety-relevant events are promptly reported to the ethics committee and the safety monitor within 24 hours.

#### **Sample size and power calculations**

The study concerns the improvement of dystonia between EG and CG in terms of BFMDRS score in the 3 months follow-up. According to the results of study, which design is basically the same as this trial. With a power setting of 80% and calculations based on two-sided 95% confidence intervals, the study required 17 pairs for GPi and 14 pairs for STN. We assume that 10% of the trial participants will be lost to attrition. Thus, a total of 70 participants need to be allocated to each treatment group.

#### **Statistical analysis**

All evaluations of effectiveness and safety will be conducted according to the intention-to-treat (ITT) principle. The final data will be analyzed using IBM SPSS 13.0 or higher (SPSS, Inc., Chicago, IL, USA) and SAS 9.4 or higher (SAS Institute Inc., Cary, NC, USA) software. A p-value < 0.05 will be considered statistically significant. Data will be analyzed with t-tests and  $\chi^2$  tests for continuous variables and categorical variables, respectively.

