#### **Handling of Missing Data**

All variables included in the CRF are mandatory. The method last visit carried forward will be used to handle the missing data.

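### The implied t-test on change in BFMDRS movement score is valid, but adjusting for the baseline score would usually give a more precise 3-month comparison

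*Protocol*

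**What the plan says.** The Statistical analysis section gives one generic sentence for all continuous variables: "Data will be analyzed with t-tests and" chi-squared tests, the latter for categorical variables. It does not name the variable tested, the time point or any covariate. No other section mentions baseline adjustment.

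Two other sections supply the missing parts. Under Primary clinical outcomes: "The primary outcome measures will focus on the changes in movement scores on the Burke-Fahn-Marsden Dystonia Rating Scale (BFMDRS"), assessed after three and six months. Sample size and power calculations concerns improvement between EG and CG at 3 months, with 80% power and two-sided 95% confidence, and states that "the study required 17 pairs for GPi and 14 pairs for STN". It then adds: "We assume that 10% of the trial participants will be lost to attrition". The total appears under Patient population and recruitment: "The study population comprises 70 patients suffering from primary dystonia".

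The design section adds that EG and CG differ in stimulation only up to 3 months: "After 3 months of stimulation in the blinded conditions, unblinding, the IPG of participants will turn ON".

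**The concern.** Put together, these sections imply an unadjusted two-sample t-test on change from baseline, EG against CG, at 3 months. No single sentence says so.

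A t-test on change subtracts the whole baseline score, which fixes the slope of the 3-month score on baseline at 1. ANCOVA estimates that slope from the data. When the true slope is not close to 1, the change score carries avoidable noise.

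The stake is efficiency. Each target is sized on its own with small arms, so any gain in precision matters most there, and it would come without another patient.

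**Working it through.** **Inputs from the protocol.** 17 pairs for GPi and 14 for STN, 80% power, two-sided 5%, 1:1 allocation, 10% attrition, 70 patients in total.

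**Assumptions.** A pair is one EG and one CG patient, so n is 17 and 14 per arm. The change-score t-test has exactly 80% power there. Neither rho nor the ratio k of 3-month SD to baseline SD is given, so both are varied.

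**1. The plan's own figure.** 17/0.9 = 18.9 and 14/0.9 = 15.6, rounded up to 19 and 16 per arm; 2 × (19 + 16) = 70. The stated total reproduces, which supports this reading of pairs.

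**2. Implied effect.** The noncentral t distribution gives 80% power at d = 0.991 (17 per arm) and d = 1.100 (14 per arm), with d in SDs of change.

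**3. Variance of ANCOVA relative to the change score.**

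ratio = k²(1 − rho²) / (1 + k² − 2k·rho) × (1 + 1/(2n − 4))

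The first factor never exceeds 1 and equals 1 when k·rho = 1. The second is the price of estimating the slope: 1 + 1/30 = 1.033 at n = 17 and 1 + 1/24 = 1.042 at n = 14. The most ANCOVA can lose is therefore about 3–4% in variance. At equal SDs (k = 1) the first factor is (1 + rho)/2.

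**4. Power at equal SDs** (noncentral t on 2n − 3 df, averaged over chance baseline imbalance):

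| | 17 / 14 per arm | 19 / 16 per arm |
|---|---|---|
| t-test on change | 80% / 80% | 84.4% / 85.3% |
| ANCOVA, rho 0.3 | 92.7% / 92.5% | 95.2% / 95.6% |
| ANCOVA, rho 0.5 | 88.8% / 88.6% | 92.2% / 92.6% |
| ANCOVA, rho 0.7 | 84.8% / 84.4% | 88.8% / 89.3% |
| ANCOVA, rho 0.9 | 80.7% / 80.3% | 85.2% / 85.8% |
| ANCOVA, rho 0.95 | 79.6% / 79.3% | 84.2% / 84.9% |

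The right-hand column assumes that all randomised patients are analysed and that carrying values forward does not dilute the effect. The protocol does plan it: "The method last visit carried forward will be used to handle the missing data".

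**5. Unequal SDs.** With k = 0.8, ANCOVA power at 17/14 per arm is 93–97% for rho from 0.3 to 0.95. With k of 1 or more, there is a band of rho in which the variance ratio exceeds 1 and ANCOVA loses:

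| k | rho, 17 per arm | rho, 14 per arm |
|---|---|---|
| 1.0 | above 0.94 | above 0.92 |
| 1.1 | 0.80–0.96 | 0.78–0.96 |
| 1.2 | 0.70–0.91 | 0.69–0.92 |
| 1.3 | 0.63–0.86 | 0.61–0.87 |

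Outside its band, each ratio gives a gain. The lost degree of freedom shifts these edges by no more than about 0.01 when judged on power. The bands must be read row by row: at k = 1.1 and rho 0.65 ANCOVA has about 83% power, and at k = 1.3 and rho 0.95 about 89%, both gains. Over k from 0.7 to 1.5 and rho from 0.3 to 0.95 the largest loss is 1.7 points (14 per arm, k = 1.4, rho 0.7).

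**6. Targets pooled.** 17 + 14 = 31 per arm. The t-test has 97.0% power at d = 0.991. At equal SDs the confidence interval shrinks by the factor √((1 + rho)/2 × 1.017): 0.873 at rho 0.5 and 0.930 at rho 0.7, so about 13% and 7% narrower.

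**The case against.** The strongest objection is one of scope. Covariate adjustment is routinely left to a statistical analysis plan, which is not at hand, and a single generic sentence is thin evidence of a fixed primary analysis. That sentence would also fit a t-test on the 3-month score itself or on the rate of improvement. This stands as far as it shows that the change-score test is inferred. It does not remove the point, because the protocol is not silent: it names a method for every continuous variable, and a later plan using ANCOVA would have to depart from that sentence.

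The second objection is that the benefit cannot be determined. This also stands. Without rho and the SDs, the result at the planned size runs from a loss of 1.7 points to a gain of about 17 (80% to 97%). The protocol does not say whether the primary test is by target or pooled, and pooling leaves little power to gain. What remains is the asymmetry: the loss is capped and the gain can be large.

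A reader might go further and infer that the planned t-test is biased or has the wrong type I error, or that the trial is underpowered because of it. The documents support neither. Randomisation protects the t-test on change, and the stated total of 70 is consistent with 80% power before the attrition allowance.

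**Conclusion.** The point holds as a matter of efficiency only. The implied unadjusted t-test on change is valid; ANCOVA on baseline is usually, not always, more precise.

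On the per-target reading with equal SDs, the gain falls from about 13 points at rho 0.3 to under 1 point at rho 0.9, and becomes a loss of under 1 point at rho 0.95. It is larger if scores are less spread at 3 months than at baseline. It is a loss of under 2 points inside the bands shown for a spread equal to or wider than baseline. On the pooled reading the benefit is mainly a narrower interval.

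These sizes rest on reading pairs as patients per arm, on 80% power for the t-test at those numbers, and on assumed values of rho and the SDs. It would be wrong to quote any one of them as the gain for this trial. The change is optional: a cheap improvement.

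**What to change.** In the Statistical analysis section, state that the 3-month EG versus CG comparison of BFMDRS movement score will be made by ANCOVA with group and baseline BFMDRS movement score as terms. Add randomised target (STN or GPi) if the targets are pooled. Report the adjusted difference with its 95% confidence interval and keep the t-test on change as a supportive analysis. Leave the 6-month outcome in place and apply the same adjustment to any between-group comparison made then. By that visit all devices are ON, so EG versus CG is no longer a comparison of ON with OFF.

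The cost is one degree of freedom (two if target is added), a possible power loss of under 2 points, and a protocol amendment with Institutional Review Board approval while the trial is enrolling. No new data are needed. A change score already requires the baseline score, and the Randomization and blinding section says that "eligible participants will be randomly assigned to one of two targets (STN or GPi) after completing the baseline measurements".
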